5.5 Dose Modification

No modification of dose is planned in Treatment Period 1.

Subjects in Treatment Period 2 at a dose of [REDACTED] mg CSL312 q4wk who experience ≥ 3 HAE attacks within an 8-week period are eligible to have their CSL312 dose increased to [REDACTED] mg CSL312 q4wk. All CSL312 dose increases will be made in eligible subjects at the discretion of the investigator in consultation with CSL. All C1-INH HAE subjects receiving the [REDACTED] mg dose will have their dose reduced to [REDACTED] mg q4wk SC at their next scheduled study visit.

6 Allocation, Dosing, and Administration

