### 4.3.2 Dose Modification

No dose modification is planned in Treatment Period 1.

Subjects in Treatment Period 2 at dose of [CCI] mg CSL312 q4wk who experience  $\geq 3$  HAE attacks within an 8-week period are eligible to have their CSL312 dose increased to [CCI] mg CSL312 q4wk. All CSL312 dose increases will be made in eligible subjects at the discretion

of the investigator in consultation with CSL. All C1-INH HAE subjects receiving the [REDACTED] mg dose will have their dose reduced to [REDACTED] mg q4wk SC at their next scheduled study visit, after the subject has signed informed consent to Amendment 2.

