## 9.2 Protocol Violations

Protocol violations are those protocol deviations which may identify subjects who should be excluded from one or more analysis population(s). Listings showing subjects with protocol deviations will be generated prior to each interim and the final analysis to identify subjects who may have these protocol violations. During the Data Review Meetings, the subject assignment to analysis populations will be discussed in detail based on the consolidated protocol deviations from the █ along with the listings of the potential protocol violations specified below. It cannot be ruled out that during the discussion of protocol deviations, additional violations which are not listed below will be considered to

have a significant impact and will thus lead to exclusion of subjects from analysis population(s). The decisions made during the Data Review Meetings will be documented in detail in the Data Review Meeting minutes and may modify the specifications in the list below. The Data Review Meeting minutes will be agreed upon prior to each interim and final analysis.

Potential Protocol Violations	Potential Exclusion From Analysis Population
Subject did not provide informed consent (informed consent date missing)	Screening, Safety, ITT, PP, PK, (b) (4)
Subject randomized but not treated with study treatment	Safety, PP, PK, (b) (4)
Subjects treated with incorrect study treatment	PP, potentially PK, (b) (4)
Subject randomized and treated but does not have at least one measurable PK concentration	PK
Subject randomized and treated but does not have at least one (b) (4) measurement	(b) (4)
Subject randomized and treated but without primary efficacy assessment	PP
Subject randomized and treated but violated inclusion or exclusion criteria	PP, potentially also PK, (b) (4)
Subject randomized and treated but compliance outside 80-120%	PP, potentially also PK, (b) (4)
Subject randomized and treated but received prohibited concomitant medication	PP, potentially also PK, (b) (4)

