## 10 Efficacy

The primary efficacy endpoint will be summarized for the ITT and PP populations. CCI

Tables will be presented by treatment as described in Section 7.2 and treatment period. The planned treatment will be used. This is the randomized treatment before planned dose reduction following Amendment 2. After planned dose reduction following Amendment 2, the planned treatment is the reduced dose (CCI mg) for the C1-INH HAE subjects randomized to CCI mg in Treatment Period 2. Unplanned dose reductions or dose increase to CCI mg CSL312 q4wk will not be considered for the Efficacy analysis.

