## 10.4 Treatment Compliance

Compliance will be summarized for the ITT population for the SC injections in each treatment period and both periods together for subjects who received the same dose continuously during both treatment periods (data will only be included until the date of the planned dose reduction following Amendment 2 in Treatment Period 2). The IV infusions will not be included in the compliance analysis. The administered volume of each injection will be taken from the data base. The study medication has a concentration of CCI mg per mL. To maintain the blind, the doses in the blinded part of Treatment Period 1 will be volume-normalized. It is planned that all SC injections will contain mL. If in the blinded study part, the subject is randomized to CCI mg CSL312, the mL injection will contain purely the study medication. For the CCI mg and the CCI mg CSL312 group, the study

medication will be diluted in a [REDACTED] and [REDACTED] ratio, respectively. For the derivation of the actual dose, it is assumed that the dilution will take place as planned. For the open-label part, the study medication is not diluted.

From the actual volume of an injection as in the database and considering the randomized dose, the actual dose will be derived as:

$$\text{Actual dose (mg)} = (\text{actual volume [mL]} / K [\text{mL/mg}]) * 100,$$

where  $K =$  [REDACTED] or [REDACTED] mL/mg for [REDACTED] mg, [REDACTED] mg, or [REDACTED] mg CSL312 q4wk in the blinded arm and [REDACTED] for the open-label arms.

Compliance for dose (mg) will be calculated as

$$\text{Compliance (\%)} = [\text{total cumulative actual dose} / \text{total planned dose}] * 100,$$

where the total planned dose will be derived from the subject's exposure and planned treatment schedule (q2wk or q4wk) as

$$(\text{duration of exposure in days} / (7 * X)) * \text{planned dose} + \text{planned dose}$$

where (duration of exposure in days) is rounded down to the nearest integer which can be divided by 7 and  $X = 2$  or  $4$  corresponds to q2wk or q4wk, respectively.

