Only the administered doses will be considered for the total cumulative actual dose which are identical to the planned treatment. The planned treatment is the randomized treatment in Treatment Period 1 and in Treatment Period 2 prior to the planned dose reduction following Amendment 2. For C1-INH HAE subjects randomized to [REDACTED] mg CSL312 in Treatment Period 2, the planned treatment after dose reduction changes to [REDACTED] mg CSL312. Exposure duration will depend on the treatment period and subject's course of the study. Definitions are provided in Section 8.2.8.

The following summaries will be provided:

- Descriptive statistics for compliance (%) over the entire treatment period, for Treatment Period 1 plus the first three doses of Treatment Period 2 (administration on site), and for Treatment Period 2 after the first three doses (administration at home);
- Number and percentage of subjects in the compliance categories < 80%, 80 – 120%, and > 120% and < 90%, 90 - 110%, and > 110% for the periods specified above.

A by-subject listing as specified in Section 7 and with the following additional information will be provided:

- Randomized, planned and actual treatments;

- Compliance in Treatment Period 1 plus the first three doses of Treatment Period 2, after the first three doses in Treatment Period 2, and over the entire study.

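### SAP 10.4 gives no compliance credit for injections after a permitted Treatment Period 2 dose increase, so adherent up-titrated subjects can fall under the 80% limit listed as a potential per-protocol exclusion

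*SAP*

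**What the plan says.** SAP 10.4 (Treatment Compliance) sets compliance as total cumulative actual dose over total planned dose, times 100. For the numerator: "Only the administered doses will be considered for the total cumulative actual dose which are identical to the planned treatment". Planned treatment is then defined: "The planned treatment is the randomized treatment in Treatment Period 1 and in Treatment Period 2 prior to the planned dose reduction". For C1-INH HAE subjects affected by Amendment 2, the planned treatment becomes the reduced dose from the reduction onward. No corresponding update is given for an increase.

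The denominator is introduced as follows: "where the total planned dose will be derived from the subject's exposure and planned treatment schedule (q2wk or q4wk) as". The formula is exposure days (rounded down to a multiple of 7) divided by 28 for q4wk dosing, times the planned dose, plus one further planned dose. Exposure is taken from SAP 8.2.8.

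Both documents permit an increase in Treatment Period 2. Protocol 5.5 covers subjects at one dose level "mg CSL312 q4wk who experience ≥ 3 HAE attacks within an 8-week period are eligible to have their CSL312 dose increased to" a higher q4wk dose, and SAP 4.3.2 repeats that they "are eligible to have their CSL312 dose increased to" that dose. For Treatment Period 1, Protocol 5.5 says: "No modification of dose is planned in Treatment Period 1".

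SAP 9.2 lists among potential protocol violations: "Subject randomized and treated but compliance outside 80-120" percent, with potential exclusion from the PP population and possibly from the PK population.

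**The concern.** The increase is part of the protocol, yet the compliance rule treats every injection given after it as if it had not been given. A subject who follows instructions exactly is then reported as having low compliance, and the compliance categories in SAP 10.4 misstate adherence for that subject.

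The subjects affected are not a random subset. They qualify for the increase by having at least 3 attacks in 8 weeks on the starting dose. If low calculated compliance led to their exclusion from a PP summary of Treatment Period 2, subjects with more attacks would be removed from the starting dose group, and its attack rate would look lower than it was. Protocol 3.3.1 says the study data will be used to select phase 3 doses, so even a descriptive distortion is worth avoiding.

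**Working it through.** The plan gives no worked compliance figure to reproduce, so the SAP formula is applied directly.

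**Inputs**
- First Treatment Period 2 dose for q4wk subjects: Day 91. Last visit without extension: Day 399 (Protocol 8.5.4).
- Doses every 28 days (Protocol 3.2.2): Days 91, 119, 147, 175, 203, 231, 259, 287, 315, 343, 371, which is 11 doses.
- Exposure (SAP 8.2.8). With no dose change, it runs from the Week 13 visit to the Study Completion Visit, plus 1. With a dose change, two portions are given, one before and one after the change.
- k = number of Treatment Period 2 doses taken before the increase.

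**Adherent subject, no increase.** 399 − 91 + 1 = 309 days, rounded down to 308. Planned doses = 308/28 + 1 = 12. Compliance = 11/12 = 92%.

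**Reading A: exposure runs through all of Treatment Period 2.** For an increase at Week 33 (Day 231), the two portions are 231 − 91 + 1 = 141 and 399 − 231 = 168 days, which sum to 309. The denominator stays at 12 and only k doses count, so compliance = k/12.

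**Reading B: exposure stops at the increase.** For Week 33, 141 days round down to 140; 140/28 + 1 = 6 planned doses; compliance = 5/6. In general, compliance = k/(k+1).

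| Increase at | k | A: k/12 | B: k/(k+1) |
|---|---|---|---|
| Week 17 (Day 119) | 1 | 8% | 50% |
| Week 21 (Day 147) | 2 | 17% | 67% |
| Week 25 (Day 175) | 3 | 25% | 75% |
| Week 29 (Day 203) | 4 | 33% | 80% |
| Week 33 (Day 231) | 5 | 42% | 83% |
| Week 49 (Day 343) | 9 | 75% | 90% |
| Week 53 (Day 371) | 10 | 83% | 91% |
| No increase | 11 | 92% | 92% |

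Every row describes a subject who took all 11 injections. Under A, all increases through Week 49 fall below 80%. Under B, only those after 1 to 3 doses do. The shortfall under B comes from the extra planned dose weighing more over a shorter stretch, and adherence after the increase is not assessed at all.

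**With planned dose following the increase.** Let r be the ratio of the increased to the starting dose. It is redacted, so the values here are assumptions. With the extra planned dose added once, at the increased level:

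compliance = [k + r(11 − k)] / [k + r(11 − k) + r]

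- r = 1.5, k = 1: 16/17.5 = 91%.
- r = 3, k = 9: 15/18 = 83%.
- r = 6, k = 1: 61/67 = 91%; k = 9: 21/27 = 78%.

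For r from 1.5 to 3 and k from 1 to 9, the score is 83% to 91%. Counted by injections, it is 11/12 = 92%.

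**The case against.** Four points can be made against this.

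*The large figures depend on Reading A.* SAP 8.2.8 reserves the undivided Treatment Period 2 exposure for subjects without a dose change, and SAP 10.4 does not say that the two portions are summed. This stands. A reader might infer that the 42% and 75% are what the SAP produces, but they are one of two readings.

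*Exclusion is not automatic.* A reader might also infer that up-titrated subjects will be dropped from PP. The documents do not say so. SAP 9.2 speaks of potential violations and potential exclusions, decided at the Data Review Meeting. That meeting would have listings of randomized, planned and actual treatment (SAP 10.4) and of dose changes (SAP 11.2). This also stands. Even so, no text exempts a permitted increase from the criterion, and the compliance tables would be wrong whatever the meeting decides.

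*The rule matches the efficacy convention.* SAP 10 says: "Unplanned dose reductions or dose increase to CCI mg CSL312 q4wk will not be considered for the Efficacy analysis". Subjects stay under their randomized dose, so a PP analysis might reasonably leave out those who spent much of the period on another dose. That is a fair purpose, but it should be stated as such. Classing these subjects as non-compliant is a different and inaccurate reason. The argument does justify confining the change to the compliance calculation.

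*The 80% limit already misfires elsewhere.* An adherent q4wk subject who goes on to Treatment Period 2 has 90 days of Treatment Period 1 exposure, rounded to 84; 84/28 + 1 = 4 planned doses against 3 given, or 75%. This is true, but it is a separate defect of the extra planned dose. It does not account for a drop from 92% to 42% under Reading A at unchanged adherence.

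**Conclusion.** The point holds as a minor one. SAP 10.4 understates compliance for fully adherent subjects who receive a permitted increase, and may put them below 80%. Against 92% without an increase, the score for an increase at Week 33 is 42% or 83%, and at Week 49 it is 75% or 90%, depending on an exposure rule that the SAP leaves open. These figures assume no extension of Treatment Period 2 and dosing exactly on schedule.

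The reach is limited to the compliance tables and any descriptive PP summary of Treatment Period 2. Such a summary follows only from the general statement in SAP 10, because SAP 10.1.2 names no population. Any PP exclusion arising this way would be related to outcome, but it remains a matter for the Data Review Meeting. The primary comparison is an ITT test in Treatment Period 1, where no dose modification is planned, so it is unaffected. The number of increases cannot be known from the documents, and SAP 9.2 does not say which period's compliance is used for PP.

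**What to change.** In SAP 10.4, for the compliance calculation only:
- Compute planned dose by portion, using the before and after dose-change portions already defined in SAP 8.2.8.
- From the date of a permitted increase, take the increased dose as the planned dose in both numerator and denominator.
- State that the extra planned dose is added once, not once per portion. Adding it in each portion would give 11/13 = 85% by injections instead of 11/12 = 92%.

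In SAP 9.2, state that a permitted increase is not in itself non-compliance. The planned-treatment convention for efficacy in SAP 10 stays as it is.

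The cost is a short SAP edit and the matching change to the compliance derivation. It needs no new data and changes no dosing rule.

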## 11 Safety Analyses

Safety data will be summarized using the Safety population. Evaluation periods for the Safety analysis are defined in Section 8.2.8.

The summary tables will be presented by actual treatment. Due to the dose increase allowed in Treatment Period 2 for subjects randomized to **cc1** mg CSL312, the unplanned dose reduction, and the planned dose reduction for C1-INH HAE subjects randomized to **cc1** mg CSL312 following Amendment 2, the same subject may occur in different dose groups in Treatment Period 2. The Total column will report each subject only once. Thus, the treatment columns will no longer sum up to the Total column. This applies to all Safety summary tables.

### 11.1 Extent of Exposure

Duration of exposure (days) will be calculated as specified in Section 8.2.8 for the duration of the safety evaluation periods. Descriptive statistics will be provided for each treatment period in which a subject participated and for the subject's exposure over the entire study.

Number and percentages of subjects who received 0 or 1 IV infusions and descriptive statistics for the number of SC injections will also be presented.

A by-subject listing will be provided as specified in Section 7 and with the following additional information:

- Duration of exposure (days) for each treatment period in which the subject participated and subject's exposure over the entire study;
- Number of IV infusions and SC injections;
- Time point and level of dose modifications.

### 11.2 Dose Modification

The number and percentage of subjects (based on the Safety population) with dose change in Treatment Period 2 will be summarized. It will be differentiated between subjects randomized to **cc1** mg or **cc1** mg CSL312 and planned or unplanned dose changes. A by-subject listing will be provided as specified in Section 7 and with date and level of dose change.

### 11.3 Adverse Events

TEAEs are AEs which start on or after the date and time of the first administration of study treatment. TEAEs with a start date and time on or after the administration of the IV loading dose and before the first administration of SC investigational product will be analyzed separately from TEAEs with start date and time on or after the first administration of SC investigational product.

AEs with completely or partially missing date or time will be considered treatment-emergent following the worst-case principle, unless the partial date clearly indicates that the AE started before the first administration of study treatment. AEs with completely missing start dates will be considered treatment-emergent. If only the day is missing, and the start month and year of the AE is before the start month and year of the first administration of study treatment, the AE will be considered non-treatment-emergent. If day and month are missing and the start year of the AE is before the year of the first administration of study treatment, the AE will be considered non-treatment-emergent.

AEs will be coded by MedDRA. There will be periodic updates of the MedDRA version. The latest licensed version will be used, and version updates will be implemented upon availability. AEs will be primarily classified by MedDRA PT. Analyses will be performed by SOC and PT. Aggregated incidences at SOC level and Any TEAE will also be provided.

TEAEs occurring until the Follow-up Visit will be summarized. All AEs regardless of when they were reported will be listed.

Summaries of TEAEs will count the number of subjects, that is, subjects with multiple occurrences of the same TEAE will be counted once in the total of those experiencing this PT. Similarly, a subject with 1 or more PT in a SOC will be counted once in the total of those experiencing PTs in that SOC. Percentages for subject incidence rates will be based on the Safety population.

CCI

CCI [REDACTED] The MedDRA SOCs and PTs will be presented in descending frequency of the overall CSL312 category. Within the same frequency, SOCs and PTs will be ordered alphabetically.

The tables referring to TEAEs on or after first SC injection will comprise two parts: one – indicated in the numbering by x.1 – containing the number of subjects, percentage of subjects, and number of events, and the other – indicated in the numbering by x.2 – containing the event rates per administration and per subject year. The tables referring to TEAEs on or after the IV loading dose and before the first SC injection will comprise only the first part (number and percentage of subjects and number of events) as described above and no rates.

AE rates per SC injection for each safety evaluation period will be calculated as follows:

- AE Rate per SC Injection =  $\frac{\text{Number of events for a particular PT}}{\text{Number of SC injections}}$

where number of SC injections will be the sum of the SC injections that subjects received during the respective safety evaluation period.

- AE Rate per Subject SC Year =  $\frac{\text{Number of events for a particular PT}}{\text{Subject SC years}}$

where subject SC years will be the sum of the time in years that subjects were exposed to study treatment administered by SC injections during the respective safety evaluation period (sum of the duration after SC injections of the respective safety evaluation period in years).

The safety evaluation periods (Treatment Period 1, Treatment Period 2, and overall) are defined for the Safety analysis in Section 8.2.8.

For TEAEs which started on or after the IV loading dose but before the first SC dose, a summary table as described below will be provided and a table of TEAEs by SOC and PT as described below.

An overview summary of TEAEs will be provided as specified in Section 7 for:

- Any TEAE;
- Any SAEs;
- Any SAEs caused by COVID-19;
- Any deaths;

- Any deaths caused by COVID-19;
- TEAEs occurring within 24 hours of investigational product administration;
- Relates TEAEs;
- TEAEs leading to study discontinuation;
- TEAEs leading to study discontinuation caused by COVID-19;
- TEAEs in each intensity category;
- TEAEs in each outcome category;
- TEAEs not resolved or resolved with sequelae caused by COVID-19.

The following summary tables will be provided as specified in Section 7 for:

- TEAEs by SOC and PT;
- TEAEs by intensity, SOC, and PT;
- Related TEAEs by SOC and PT;
- TEAEs leading to study discontinuation by SOC and PT;
- Non-serious TEAEs by SOC and PT;
- Laboratory Findings reported as AEs.

The relationship between MedDRA SOC, PT, and Verbatim Text will be listed.

TEAEs will be listed for the Safety population. AEs without specification for treatment-emergency will be listed for all data available. The listings will include the variables as specified in Section 7 and in addition MedDRA SOC, PT, and the verbatim, AE start and end date and time if available, duration of AE in days, intensity, serious (yes or no), relationship to treatment (yes or no), outcome, action taken, and AE flags (TEAE, SAE, temporal relationship within 24 hours, laboratory finding, AESI).

The following listings will be provided:

- Non-TEAEs – all data available;
- TEAEs on or after IV loading dose and before first SC dose – Safety population;
- TEAEs on or after first SC dose – Safety population;
- AEs related to laboratory findings – all data available;
- AEs caused by COVID-19;
- MedDRA SOC and PT with all AE verbatim – all data available.

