2.2.2 Secondary Endpoints

Table 2 Secondary Endpoints

Secondary Objective	Secondary Endpoints	Summary Measure(s)
1	Responder subjects.	The number and percentage of subjects with C1-INH HAE who respond to treatment with CSL312 or placebo during Treatment Period 1, where “response” is defined as a $\geq 50\%$ relative reduction in the time-normalized number of HAE attacks (per month) compared to each subject’s time-normalized

Secondary Objective	Secondary Endpoints	Summary Measure(s)
		number of HAE attacks (per month) during the Run-in Period.
1	HAE attack-free subjects.	The number and percentage of subjects with C1-INH HAE who do not experience an HAE attack on treatment with CSL312 or placebo during Treatment Period 1.
1	HAE attacks.	The number, time-normalized number (per month), and percentage of mild, moderate, or severe HAE attacks in subjects with C1-INH HAE on treatment with CSL312 or placebo during Treatment Period 1.
1	HAE attacks treated with on-demand HAE medication.	The number, time-normalized number (per month), and percentage of mild, moderate, or severe HAE attacks in subjects with C1-INH HAE treated with on-demand HAE medication on treatment with CSL312 or placebo during Treatment Period 1.
2	CSL312 PK in plasma: 
 • Maximum concentration (C_{max}). • Area under the concentration-time curve in 1 dosing interval ($AUC_{0-\tau}$). • Time of maximum concentration (T_{max}). • Terminal elimination half-life ($T_{1/2}$). • Total systemic clearance (CL_{tot}). 	CSL312 concentration in plasma in subjects with C1-INH HAE during treatment with CSL312 or placebo at specified time points during Treatment Period 1.

Secondary Objective	Secondary Endpoints	Summary Measure(s)
	
Volume of distribution during the elimination phase (V_z).	
3	Subjects experiencing: 
AEs.SAEs.AEs of special interest (ie, anaphylaxis, TEEs, and bleeding events).ISRs.Inhibitory antibodies to CSL312.Clinically significant abnormalities in laboratory assessment that are reported as AEs.	The number and percentage of subjects with C1-INH HAE experiencing the specified safety events on treatment with CSL312 or placebo during Treatment Period 1.

Abbreviations: AEs = adverse events; HAE = hereditary angioedema; C1-INH HAE = Hereditary angioedema with C1-esterase inhibitor deficiency; ISRs = injection site reactions; SAEs = serious adverse events; TEEs = thromboembolic events.

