10.3.3 Safety Analyses

AEs with a start date and time on or after the first injection date and time of investigational product are considered treatment-emergent AEs. AEs with missing or partial start date or time will also be considered treatment-emergent following the worst case principle, unless the partial date clearly indicates that the AE started before first injection date and time.

Adverse events with a start date occurring after administration of IV investigational product and occurring before the first administration of SC investigational product will be analyzed separately from AEs with a start date occurring after the first administration of SC investigational product.

Only treatment-emergent AEs will be included in analyses, although all AEs will be listed. The following tables will be presented for AEs occurring at any dose:

- Summary of subjects with AEs (number with any AE, with AEs occurring within 24 hours of investigational product injection, with SAE, with related AE, with AEs leading to study discontinuation, with each intensity, and with each outcome).

- Summary of subjects with SAEs (number with any SAE, with SAEs occurring within 24 hours of investigational product injection, with related SAE, with SAEs leading to study discontinuation, with each intensity, and with each outcome).
- Incidence of subjects with AEs by system organ class (SOC) and preferred term.
- Incidence of subjects with SAEs by SOC and preferred term.
- Incidence of subjects with AEs by severity and SOC and preferred term.
- Incidence of subjects with AEs by relationship to investigational product and SOC and preferred term.
- Incidence of subjects with AEs leading to discontinuation by SOC and preferred term.
- Incidence of subjects with TEEs by SOC and preferred term.
- Incidence of subjects with bleeding events by SOC and preferred term.
- Incidence of subjects with anaphylaxis by SOC and preferred term.
- The number of subjects experiencing AEs which occur in at least 1 treatment in at least 1, 2, 3, 4 and 5% of events will also be presented.

Summaries will include the number and percentage of subjects, the number of AEs, and the number of AEs per injection and per subject year (where applicable).

A summary of non-serious AEs only will be presented by treatment and also by SOC, preferred term, and treatment.

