**Treatment Period 1 (CCI [REDACTED]):**

Week 13 Day 85 Visit date and time – 1 – Week 1 Day 1 Visit of Treatment Period 1 date and time (the date / time of first SC administration of investigational product in Treatment Period 1) + 1.

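### No Treatment Period 1 adverse event table is specified that counts subjects from the first administration by any route, although the secondary safety endpoint covers the whole period

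*SAP*

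**What the plan says.** Protocol 2.2.2, Table 2, sets the safety summary measure as the number and percentage of C1-INH HAE subjects "experiencing the specified safety events on treatment with CSL312 or placebo during Treatment Period 1". It makes no exception for the loading-dose week.

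SAP 11.3 defines treatment emergence from the first dose by any route: "TEAEs are AEs which start on or after the date and time of the first administration of study treatment". It then divides these events at the first SC dose. Those starting after the IV dose and before the first SC dose "will be analyzed separately from TEAEs with start date and time on or after the first administration of SC investigational product". Protocol 10.3.3 sets the same division: the IV-window events "will be analyzed separately from AEs with a start date occurring after the first administration of SC investigational product".

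For the IV window, SAP 11.3 promises that "a summary table as described below will be provided and a table of TEAEs by SOC and PT as described below", plus a listing. It adds that "The tables referring to TEAEs on or after the IV loading dose and before the first SC injection will comprise only the first part", meaning subject counts, percentages and event counts without rates. The post-SC tables carry counts and also rates per SC injection and per subject SC year. No table in the readable text of SAP 11.3 spans both windows.

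SAP 8.2.8 starts the adverse event period at Day 6 for subjects given an IV dose. For the arm that begins SC dosing on Day 1, it starts at "the date / time of first SC administration of investigational product", which is there the Week 1 Day 1 Visit. The exposure period in the same section starts at the first administration by any route.

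**The concern.** The endpoint and the tables cover different periods. A reader who wants the proportion of subjects in an arm with, say, a related event during Treatment Period 1 finds two counts that may overlap, and no total.

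The separated window is short, but it contains the first exposure in every q4wk arm and the only IV exposure in the trial. Protocol 1.4 names hypersensitivity and anaphylaxis as potential risks, and Protocol 9.1.2 makes anaphylaxis an event of special interest.

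Two further gaps follow.

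- Under Protocol 7.1, anaphylaxis causally related to the product is a contraindication to further dosing. A subject who reacts to the IV dose may therefore never receive an SC dose. That subject remains in the Safety population, which is the percentage denominator, but cannot enter a post-SC numerator.
- SAP 11.4, 11.5 and 11.7 do not say which window they use. This matters most for criterion (d) of the adverse drug reaction definition, which compares exposure-adjusted rates between active arms, the open-label part included, and placebo.

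**Working it through.** The plan gives no figure of its own on this point. The check uses its visit days, period formulas and arm sizes.

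**Inputs.** q4wk arms, placebo included: IV on Day 1 and SC on Days 6, 35 and 63, with the period ending at Day 91. q2wk arm: SC on Days 1, 15, 29, 43, 57 and 71, with the period ending at Day 85. Formulas are from SAP 8.2.8. There are 8 subjects per q4wk arm and up to 8 in the q2wk arm.

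**1. Window lengths (nominal days, subjects continuing to Treatment Period 2)**

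- q4wk exposure: 91 − 1 − 1 + 1 = 90.
- q4wk adverse event period: 91 − 1 − 6 + 1 = 85.
- q2wk exposure and adverse event period: 85 − 1 − 1 + 1 = 84 for both.

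The q4wk post-SC window leaves out 90 − 85 = 5 days (5/90 = 5.6%) and 1 of 4 administrations (25%). The q2wk window leaves out 0 of 84 days and 0 of 6 administrations.

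**2. Whole-period count from two tables.** If k1 subjects appear in the IV-window table and k2 in the post-SC table, the number affected lies between max(k1, k2) and min(8, k1 + k2).

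| k1 | k2 | Subjects affected | Percent of 8 |
|---|---|---|---|
| 1 | 1 | 1 to 2 | 12.5 to 25 |
| 2 | 3 | 3 to 5 | 37.5 to 62.5 |
| 3 | 4 | 4 to 7 | 50 to 87.5 |

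Only the listings would settle it. A subject whose sole event falls in the IV window moves the whole-period figure by 1/8 = 12.5 percentage points relative to the post-SC table.

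**3. IV-only subject.** With one such subject among 8, the post-SC percentage cannot exceed 7/8 = 87.5%. The SAP 8.2.8 duration formula for IV-loaded subjects runs from the first SC administration, a date this subject does not have.

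**4. Adverse drug reaction criterion (d).** SAP 11.7 does not define its rate. Suppose it is the per-subject-SC-year rate of SAP 11.3. For illustration, assume 8 completers per arm and exactly one event in each arm, starting after the first dose and before Day 6.

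- q2wk: 8 × 84 / 365.25 = 1.84 years, so the rate is 1/1.84 = 0.54 per year.
- Placebo, post-SC window: the event is outside the window, so the rate is 0. The q2wk event meets the 30% excess condition.
- Placebo, any-route window: 8 × 90 / 365.25 = 1.97 years, so the rate is 1/1.97 = 0.51. The q2wk excess is 90/84 − 1 = 7.1%, below 30%.

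The same single event per arm is flagged or not according to a window that the SAP leaves unstated. On the post-SC rate, criterion (d) also cannot flag an event confined to the loading-dose window of a q4wk arm.

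**The case against.** The strongest defence is that nothing is lost and the split was planned. Loading-dose events appear by arm in an overview, which has rows for serious, related, within-24-hour, intensity and outcome categories, then in a SOC/PT table and in a listing. The protocol set the split, so the SAP does not depart from it. SAP 8.2.8 describes its periods as durations for denominators, and a Day 6 start suits rates per SC injection and per SC year. All of this stands.

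A reader might infer more than the documents support:

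- *That first-dose reactions in the q4wk arms are dropped, or that the endpoint is never produced.* The events are in the IV-window tables. SAP 11.4, 11.5 and 11.7 and the interim list in SAP 4.6.1 state no split, and Protocol 10.3.3 introduces its list with "The following tables will be presented for AEs occurring at any dose". Some of those tables may span both windows. Part of SAP 11.3 is redacted and the table shells are in a separate document, so the accurate statement is that no combined table is specified in the text available.
- *That the comparison with placebo is biased.* All four blinded arms receive an IV dose and follow the same rule. Only the open-label q2wk arm starts its window differently, and it is reported separately and not tested against placebo.
- *That every part of the endpoint is affected.* Laboratory and antibody results are summarised by visit. In the q4wk schedule the safety laboratory samples are taken before dosing on Day 1 and next on Day 35. Injection site reactions relate mainly to SC dosing.
- *That IV-only subjects vanish.* All their treatment-emergent events precede any SC dose and fit the IV-window tables.

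None of this supplies the whole-period subject count, or the missing statement of window.

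**Conclusion.** The point holds as a reporting gap. SAP 11.3 specifies no Treatment Period 1 table that counts subjects from the first administration by any route, so the incidence named in Protocol Table 2 is not given by any table specified there and cannot be rebuilt by adding the two that are. The uncertainty can span several subjects in an arm of 8, as in the 4-to-7 example. The window concerned is 5.6% of nominal days but a quarter of the q4wk administrations.

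The window for SAP 11.4, 11.5 and 11.7 is ambiguous rather than wrong. The mismatch in criterion (d) is conditional on its using the SC-based rates.

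These conclusions assume nominal visit days and that the redacted text and separate shells do not already provide a combined table. Event counts in the examples are hypothetical. Severity is low to moderate: the data are collected and listed, and the randomised safety comparison is unaffected.

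**What to change.** In SAP 11.3 to 11.7:

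- Add Treatment Period 1 incidence tables that run from the first administration by any route: overview, SOC/PT, intensity, related, serious events, each event of special interest, and adverse drug reactions.
- Keep the IV-window and post-SC tables as sub-displays, and leave the per-SC-injection and per-SC-year rates as they are.
- State that 11.4, 11.5 and 11.7 use the any-route window, and that criterion (d) starts at the first administration in every arm.
- State that subjects dosed IV but never SC are counted in these tables.

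The cost is SAP wording and a few extra runs of tables already planned, with an earlier start date. Trial conduct does not change, and Protocol 10.3.3 can stand because the separate displays remain. Aligning the windows does not make the q2wk arm a randomised comparator, so its results should still be read as open-label and descriptive.
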